9.4 DATA SOURCES

Variables collected at the time of the study visit (including those related to the time of the first NOAC initiation) will be obtained based on and limited to those available in the medical records of the selected patients.

Demographic characteristics, smoking habit and alcohol consumption may be asked to the patient at the study visit if not available in the medical records.

The variables used to determine the kidney and liver function, as well as the hemoglobin and platelet levels can be obtained from the last analytical results available in the medical charts. Creatinine clearance will be automatically determined with the serum creatinine if the Cockcroft-Gault calculation is not available in medical charts. LVEF measurement will be obtained from the last images available for the patient.

Clinical Frailty Scale (19), Modified EHRA scale for AF related symptoms (23) and NYHA classification (24) (Refer to Annex 3 for these scales), CHA2DS2-VASc, HAS-BLED scores, will be assessed by the investigators at the study visit by evaluating the patient’s functional status and medical records and the values will be directly included in the eCRF.

Final score for the Comorbidities Charlson Index (25) will be automatically calculated based on the answers individually entered by the investigator in the eCRF for each index item.

Any required missing data to calculate the score for the scales or the Comorbidities Charlson Index may be asked to the patient at the study visit if not available in the medical records and should be documented, however the final score number obtained by the investigator from this information will not need to be included in medical records.

9.5 STUDY SIZE

It is planned that a total of approximately 500 patients will be recruited for the study. Based on such a sample size estimate, categorical variables of binomial proportions (e.g. sex) will be estimated with the precision (i.e. width of descriptive 95% confidence interval) described in the following Table 4. Calculations of the confidence intervals (CI) are based on the Clopper-Pearson method:

Table 4 Width of 95% confidence interval by prevalence of attribute:

Prevalence of attribute	Sample size
	500
10% Expected n	50
95% CI width	5.46%
20% Expected n	100
95% CI width	7.20%
30% Expected n	150
95% CI width	8.22%
40% Expected n	200
95% CI width	8.76%
50% Expected n	250
95% CI width	8.94%

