9.3.2 Outcomes

9.3.2.1 Primary outcome

The primary outcome is the pattern of usage of non-vitamin K oral anticoagulants (NOACs) prescribed according to their Summary of Product Characteristics (SmPC), based on the percentage of patients by NOAC type and dose the patient is taking at the time of the study visit. Timeframe to complete data collection for this outcome is one day, the study visit day.

Table 2 Primary variable collected at the time of the study visit

[figure not shown]
Variable	Obtained from medical records
Current NOAC active substance and dose	x

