14.1.1 Primary Analysis of Primary Outcome

The primary outcome analysis will be performed for the FAS. For the primary objective, the pattern of usage of NOAC will be described as the percentage of patients by NOAC type and dose.

The pattern of NOAC usage will be also analyzed descriptively by the following subgroups, if a minimum of 50 patients have been included in the required subgroups:

- Sex (female, male)
- Age at the time of the study visit (75-79, 80-84, ≥ 85 years)
- Comorbidities at the time of the study visit: heart failure, coronary artery disease, peripheral vascular disease, diabetes, chronic kidney disease, liver disease and cancer.

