17.3 Outcomes

17.3.1 Primary outcome: Current NOAC

Table 27. Type of NOAC, dose and duration since first NOAC initiation at study visit according to sex

		Male	Female	Total
Current NOAC	Valid N Dabigatran Rivaroxaban Apixaban Edoxaban N missing			
Dabigatran dose	Valid N 110mg BID 150mg BID N missing			
Rivaroxaban dose	Valid N 15mg QD 20mg QD N missing			
Apixaban dose	Valid N 2.5mg BID 5mg BID N missing			
Edoxaban dose	Valid N 30mg QD 60mg QD N missing			

Document: H:\HOR-Europe\2019\2512352 - Study on anticoagulation management - BI\Proyecto\Estadística\SAP\S AP_REBELD_version1.0_08072020.docx

Author: Version Number: Version 1.0
Version Date: [08072020]

Template No.: RWI_TP_BIOS0013 Revision 1

Reference: RWI_WI_BIOS0015

Effective Date: 15Jun2018

		Male	Female	Total
Years since first NOAC initiation to study visit	Valid N Mean (SD) Median (Q1-Q3) Min-Max N missing			

BDI: twice a day; QD: once a day

Table 28. Type of NOAC, dose and duration since fist NOAC initiation at study visit according to age

		75-79 years	80-84 years	≥85 years	Total
Current NOAC	Valid N Dabigatran Rivaroxaban Apixaban Edoxaban N missing				
Dabigatran dose	Valid N 110mg BID 150mg BID N missing				
Rivaroxaban dose	Valid N 15mg QD 20mg QD N missing				
Apixaban dose	Valid N 2.5mg BID 5mg BID N missing				
Edoxaban dose	Valid N 30mg QD 60mg QD N missing				
Years since first NOAC initiation to study visit	Valid N Mean (SD) Median (Q1-Q3) Min-Max				

Document: H:\HOR-Europe\2019\2512352 - Study on anticoagulation management - BI\Proyecto\Estadística\SAP\S
AP_REBELD_version1.0_08072020.docx

Author: [REDACTED] Version Number: Version 1.0
Version Date: [08072020]

Template No.: RWI_TP_BIOS0013 Revision 1

Reference: RWI_WI_BIOS0015

Effective Date: 15Jun2018

		75-79 years	80-84 years	≥85 years	Total
	N missing				

BDI: twice a day; QD: once a day

Table 29. Type of NOAC, dose and duration since fist NOAC initiation at study visit according to heart failure

		Heart failure		
		No	Yes	Total
Current NOAC	Valid N Dabigatran Rivaroxaban Apixaban Edoxaban N missing			
Dabigatran dose	Valid N 110mg BID 150mg BID N missing			
Rivaroxaban dose	Valid N 15mg QD 20mg QD N missing			
Apixaban dose	Valid N 2.5mg BID 5mg BID N missing			
Edoxaban dose	Valid N 30mg QD 60mg QD N missing			
Years since first NOAC initiation to study visit	Valid N Mean (SD) Median (Q1-Q3) Min-Max N missing			

BDI: twice a day; QD: once a day

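### The study-size precision holds for whole-sample percentages such as NOAC type, but not for the primary dose percentages, which the SAP tables indicate are calculated within each NOAC

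*Protocol*

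**What the plan says.** Protocol 9.5 sets the size: "It is planned that a total of approximately 500 patients will be recruited for the study". It then states that "categorical variables of binomial proportions (e.g. sex) will be estimated with the precision" shown in Table 4, where precision means the "width of descriptive 95% confidence interval". The method is named: "Calculations of the confidence intervals (CI) are based on the Clopper-Pearson method". The table has one sample-size column, 500, and the example variable is sex. SAP 4.2 repeats the statement and reprints the table as SAP Table 1.

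The primary outcome (Protocol 9.3.2.1) is the pattern of NOAC use, "based on the percentage of patients by NOAC type and dose the patient is taking at the time of the study visit". The mock tables for it are SAP Tables 27 to 35. Each opens with one block for drug type, "Valid N Dabigatran Rivaroxaban Apixaban Edoxaban N missing", and then has a separate block for each drug's dose. The dabigatran block reads "Valid N 110mg BID 150mg BID N missing", and the other three drugs have the same layout.

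SAP 14.1.1 adds breakdowns by sex, age and comorbidity "if a minimum of 50 patients have been included in the required subgroups". Protocol 9.9 concedes reduced precision for some subgroup analyses and gives no figure. Neither document gives an expected number of patients per NOAC, and Protocol 9.2 describes consecutive enrolment without a quota by drug.

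**The concern.** The study tests no hypothesis, so Table 4 is the whole justification of its size. The sentence introducing it speaks of binomial variables in general and does not restrict the figures to percentages taken over the full sample. Each drug's dose split is a two-level binomial variable and belongs to the primary outcome, but its denominator appears to be the users of that drug.

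If so, the document justifies its size with a precision that the dose part of its primary outcome will not have. Dose is not a side issue here, because the rationale in Protocol section 7 rests partly on under-dosing in elderly patients. The results tables may not correct the impression. The protocol abstract promises 95% confidence intervals as appropriate, but Tables 27 to 35 have no interval row and SAP 8.2 specifies none. Table 4 could be the only statement of precision a reader meets.

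**Working it through.** **Inputs.** Total n about 500, two-sided 95% Clopper-Pearson interval, precision as full width (all Protocol 9.5). Four NOACs, each dose split with its own Valid N (SAP 17.3.1). Group sizes per NOAC are not in the documents and are assumed below.

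**Formula.** For x patients out of n, lower = Beta quantile(0.025; x, n−x+1), upper = Beta quantile(0.975; x+1, n−x), width = upper − lower, with x = n × prevalence rounded to a whole number.

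**Step 1: reproduce Protocol Table 4 (n=500).**

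| Prevalence | x | Interval | Width from rounded limits | Unrounded width | Protocol Table 4 | SAP Table 1 |
|---|---|---|---|---|---|---|
| 10% | 50 | 0.0751 to 0.1297 | 5.46 | 5.46 | 5.46 | 5.46 |
| 20% | 100 | 0.1658 to 0.2378 | 7.20 | 7.20 | 7.20 | 7.20 |
| 30% | 150 | 0.2601 to 0.3423 | 8.22 | 8.21 | 8.22 | 8.22 |
| 40% | 200 | 0.3568 to 0.4444 | 8.76 | 8.77 | 8.76 | 8.76 |
| 50% | 250 | 0.4553 to 0.5447 | 8.94 | 8.94 | 8.94 | **8.76** |

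Protocol Table 4 reproduces; the 0.01 differences at 30% and 40% come from rounding the limits before subtracting. Wald (5.26 at 10%, 8.77 at 50%) and Wilson (5.27, 8.73) do not match, so the named method was the one used. SAP Table 1 repeats its 40% value in the 50% row.

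**Step 2: what holds for any split.** If four groups share 500 patients, the smallest cannot exceed 500/4 = 125. At n=125 the widths for 10, 20, 30, 40 and 50% are 11.1, 14.7, 16.8, 17.8 and 18.1 points. Dividing by the n=500 widths gives ratios of 2.03 to 2.04, and smaller groups give larger ratios. As a rough check, width scales with 1/√n and √(500/125) = 2.

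**Step 3: illustrative widths within one NOAC (group sizes assumed).**

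| Users of the NOAC | Width at 10% | Width at 50% | Ratio to n=500 |
|---|---|---|---|
| 500 (as stated) | 5.46 | 8.94 | 1 |
| 250 | 7.8 | 12.7 | 1.4 |
| 125 (equal four-way split) | 11.1 | 18.1 | 2.0 |
| 100 | 12.7 | 20.3 | 2.3 |
| 50 | 18.5 | 28.9 | 3.2 to 3.4 |

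**The case against.** Four points can be made on the other side.

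- **Table 4 is not wrong.** It is labelled for 500 patients and uses sex as its example. This stands: the gap is one of scope, and the NOAC-type percentages, taken over the full analysis set, do have the stated precision. A reader might infer that the sample-size arithmetic failed; it did not.
- **The denominator is inferred.** The protocol's wording could mean type-by-dose cells out of all patients, to which Table 4 would apply. The SAP states its percentage base for some tables (Table 52 and the adverse reaction tables) but not for Tables 27 to 35. This stands as a caveat. A separate Valid N for each drug nevertheless makes the within-NOAC reading much the more likely one.
- **Subgroup imprecision is already disclosed.** Protocol 9.9 covers it, so very wide intervals for one NOAC within a small sex, age or comorbidity group should not be held against the primary result. The point here concerns only the Total column, which is not a subgroup and which 9.9 does not mention.
- **The study is descriptive and the tables print each denominator.** No decision rule depends on Table 4, which limits the harm. But with no test to power, precision is the only argument for the study size, and it should cover the primary estimates.

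A reader might also infer that every dose percentage is two to three times less precise than stated, or carries an error of ±9 to ±14 points. The documents do not support that. A factor of two to three needs roughly 60 to 125 users per NOAC, and ±9 to ±14 further needs a prevalence near 50%. A drug with 250 users would be only 1.4 times wider, about ±6.4 at 50% (12.7/2).

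**Conclusion.** The point holds as a gap in the precision statement. Table 4 is correct for n=500 and valid for NOAC type, but Protocol 9.5 and SAP 4.2 present it as the precision of binomial variables generally, and it does not describe dose within NOAC. No dose split has the stated precision unless a single drug accounts for the whole sample.

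The one size that does not depend on an assumed split is this: with four NOACs in use and about 500 patients, at least one dose percentage has a 95% interval about twice as wide as stated, or wider. It rests on the within-NOAC reading of Tables 27 to 35 and on all four drugs having users. All other widths are illustrations for assumed group sizes. The matter affects stated precision only; it does not affect power, design or the validity of the planned percentages.

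**What to change.** Keep n=500. In Protocol 9.5 and SAP 4.2, state that the 500 column applies to proportions over the whole sample, such as NOAC type. Add columns for n = 250, 125, 100 and 50 to Protocol Table 4 and SAP Table 1, labelled as assumed group sizes, and name them as the precision for dose within NOAC. In the same edit, correct the 50% row of SAP Table 1 from 8.76% to 8.94%.

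There is no need for a rule withholding percentages in dose blocks with fewer than 50 users. That would be a matter of preference, and it could remove a primary percentage for a less-used drug; a wide estimate with its denominator shown is acceptable in a descriptive study.

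The work is a sentence and four table columns in each document. The downside is that the stated precision becomes less favourable.

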9.6 DATA MANAGEMENT

The data will be entered by the investigators themselves and/or authorized personnel directly in the electronic case report form (eCRF). A data management plan (DMP) will be created to describe the method and procedure for each data management step for the study, from electronic Case Report Form (eCRF) design up to final database delivery.

The eCRFs will include programmable edit checks to obtain immediate feedback if data are missing, out of range, illogical or potentially erroneous. The Edit Checks Specifications (Data Validation Plan (DVP)) is included in the eCRF specification documentation. These checks will be performed once data is entered into the eCRF. Thus the data entered into the eCRF will be validated within the system and the physician will receive alerts for missing or inconsistent data. In case any changes of already entered data will be required, an audit trail will be available.

AE reconciliation will be performed quarterly from study initiation date.

Data quality reviews are planned to be performed in the study with the purpose of data cleaning and to detect possible quality issues in advance. Details will be explained in the NIS Monitoring Manual.

When data management is outsourced, the designated contract organization will be responsible for the development and implementation of the data management and validation plans.

The database will be housed in a physically and logically secure computer system maintained in accordance with a written security policy. The system will meet the standards of the International Committee on Harmonization guideline E6R1 regarding electronic study data handling. Patient confidentiality will be strictly maintained.

9.7 DATA ANALYSIS

Analyses will be performed by Boehringer Ingelheim's designees.

In this non-interventional study, retrospective data from medical charts and data at the study visit will be collected for non-valvular AF patients. Once the study has been completed and all data from the last patient have been recorded, the database will be closed and statistical analysis will be performed.

The proposed methods for statistical analysis presented below are a summary of the methods that will be applied in the study to analyze the data collected and to answer the study objectives.

Since the study is descriptive, the variables included in the study objectives will be summarized overall and by factors of interest. All results will be summarized with measures

of central tendency (mean and median), variability/dispersion (standard deviation and interquartile ranges), absolute and relative frequencies, and ranges.

A Statistical Analysis Plan (SAP), will be prepared to describe all processes, treatment and specifications for the planned statistical analysis.

9.7.1 Main analysis

All eligible patients (all enrolled patients fulfilling all inclusion criteria and no exclusion criteria) will be included in the analysis. Missing data will not be imputed. Number of missing values will be presented for each outcome.

For the primary objective, the pattern of usage of NOAC will be described as the percentage of patients by NOAC type and dose.

For the secondary objectives, the following descriptive analyses are planned:

1. Patient's characteristics at the time of the study visit will be summarized descriptively by current NOAC type. 
 All covariates related to patient's characteristics (refer to [Section 9.3.3](#), [Table 3](#)) will be analyzed descriptively by NOAC type and by the duration since the first NOAC initiation. Standardized differences between Pradaxa[®] and other NOACs will be estimated for these covariates. For this, a minimum of 50 patients is required for each group.
2. For OAC treatment management, descriptive analysis of previous VKA treatment (yes/no), VKA treatment duration in years, reason for switch to NOAC, first NOAC treatment duration, first NOAC dose and dose changes, new NOAC treatment duration, new NOAC dose and dose changes. Duration since NVAF diagnosis until first NOAC initiation and total time in NOAC treatment will be described. Also, the reason for switches, the number of patients that switched their first or further NOAC and mean number of switches will be presented. Antiplatelet use will be also summarized.

3. Clinical Frailty Scale grading at the time of the study visit by current NOAC type will be described as the number of patients on each category of frailty ([19](#)) as evaluated by the investigator according to patient's records. In addition, CFS score will be summarized in

the following two categories: Frailty patients (CFS scoring >4) and Non-frailty patients (CFS scoring ≤4).

4. First NOAC usage will be described by NOAC type, for primary prevention or secondary prevention, at the time of first NOAC initiation.

9.8 QUALITY CONTROL

The NIS monitoring manual will define all aspects related to the monitoring activities for the study, to ensure that it is performed in a manner that will provide meaningful data, the rights and well-being of the study patients are protected, and the conduct of the study is compliant with protocol and all applicable regulation.

All relevant issues, including protocol deviations, detected during the study will be handled and followed-up until their resolution or closure. A register of the issues and related actions will be kept.

On-site and remote monitoring will be performed by a Contract Research Organisation (CRO) appointed by BI.

Source data verification in a sample of sites is planned for this study and detailed in the monitoring manual.

Strict and continuous quality control will be maintained to ensure the accuracy and scientific rigor of the data obtained, maintaining uniform conditions for collecting the information. Quality control will be carried out by qualified personnel designated for this purpose.

A quality assurance audit/inspection of this study may be conducted by the sponsor or sponsor's designees or by Independent Ethics Committee (IECs) or by regulatory authorities. The quality assurance auditor will have access to all medical records, the investigator's study-related files and correspondence, and the informed consent document of this study.

All study relevant documentation will be stored in the study master file (SMF). In addition, each site will have an Investigator Site File (ISF) containing all study documents relevant for the site. Relevant documentation on the participating investigators, including their curricula vitae, will be filed in ISF.

9.9 LIMITATIONS OF THE RESEARCH METHODS

A NIS is the most suitable design to obtain information about the use of medicines in everyday therapeutic practice and thus for investigating questions in everyday therapeutic practice. However, there are some limitations inherent to this design.

Variables collected at the time of the study visit will be obtained based on and limited to those available in the medical records of the selected patients (refer to [section 9.4](#))

Consecutive enrolment will be employed to minimize selection bias. The entry criteria are less restrictive than the ones of a randomized clinical trial, which will permit the enrolment of a broader patient population.

The choice of NOAC was done before the study visit and it is done at the discretion of the investigator. However, patients seen by their physician less than twice per year are therefore less likely to be included in the study. Patients with higher frequency of visits are more likely to be included in the study and could be over-represented in the sample.

Due to regulatory requirements, patients are not allowed to start the NOAC treatment on the study visit date. For this, a minimum of three months of NOAC treatment before study participation has been established, which limits the NOAC population.

As patients are included after first NOAC initiation and need to be treated by a NOAC at the time of enrolment, any patient having prematurely discontinued any NOAC treatment between the time of first NOAC initiation and the start of the enrolment period will not be included in the study. The sample may therefore not be representative of all patients having initiated a NOAC. Besides, sample size may be limited for some of the planned subgroup analyses, resulting in decreased precision.

Channeling bias is a form of confounding that occurs when a drug is preferentially prescribed to patients with different baseline characteristics. Standardized differences will be applied when assessing channeling bias.

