9.3.3 Covariates

The following covariates, related to the secondary outcome, will be collected from medical records or at the study visit (refer to [section 9.4](#)) to describe the patient's characteristics:

Table 3 Patient characteristics at the time of the study visit

Variable*	Obtained from medical records	Obtained at the study visit
Demographic characteristics: Age, sex, height, weight, BMI, caregiver (Yes/No), place where patient is living (Home alone; At home with partner/other family member/a friend; Other's home (e.g family member's); Nursing home)	x	x
Smoking habit (past/current/non-smoker) and alcohol consumption (casual/habitual/abuse/dependence)	x	x
Analytical lab results (from last available blood sample analysis): - Kidney function: serum creatinine (mg/dl), creatinine clearance (Cockcroft-Gault calculation) - Liver function: AST/ALT, total bilirubin - Hemoglobin and platelet levels	x	
NVAF: - Diagnosis date (month and year) - Type (persistent, long standing persistent, permanent, paroxysmal) - Modified EHRA scale for AF related symptoms (23) (Refer to Annex 3).	x	x (mEHRA scale)
Procedures and interventions: - Cardioversion/Ablation (Yes/No) - Coronary interventions (Yes/No): Percutaneous coronary intervention (PCI)/Coronary Artery Bypass Grafting (CABG) - Pacemaker carrier (Yes/No)	x	
History of thromboembolic events (Yes/No, number): TIA, ischemic stroke, hemorrhagic stroke, embolism systemic, deep vein thrombosis, pulmonary embolism, stable angina, unstable angina, myocardial infarction with/without ST segment elevation; and bleeding events (Yes/No): intracranial, digestive, genitourinary, gingival, nasal, pulmonary, articular-muscular, conjunctival.	x	
Other concomitant treatments (Total number of current concomitant drugs; Type (Yes/No, number): ARB or ACE inhibitor, Beta-blocker, Calcium channel blockers, Diuretics, Amiodarone, Statin, Proton pump inhibitor, H2-	x	

Variable*	Obtained from medical records	Obtained at the study visit
receptor antagonist, , Digoxin, NSAIDs, Verapamil / Dronedaron, Other antiarrhythmics, ketoconazole systemic), ciclosporine, itraconazol)		

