Comorbidities and Clinical Risk Factors: - Heart Failure (Yes/No, New York Heart Association (NYHA) classification; Left Ventricular Ejection Fraction, LVEF, %) - Coronary artery disease (Yes/No) - Sleep apnoea-hypopnoea syndrome (SAHS) (Yes/No) - Hypertension (Yes/No) -Hyperlipidemia (Yes/No) - Comorbidity Charlson index (Yes/No; total score): myocardial infarction (already collected for history of thromboembolic events), congestive heart failure (already collected for the NYHA scale scoring), cerebral and peripheral vascular disease, dementia, chronic obstructive pulmonary disease, connective tissue disease, peptic ulcer disease, mild/moderate/severe liver disease, diabetes, diabetes with end-organ damage, hemiplegia, moderate/severe renal disease, any solid tumor, metastatic solid tumor, leukemia, lymphoma AIDs, age (already collected as a demographic characteristic). -History of thromboembolic events (Yes/No, number and date): TIA, ischemic stroke, hemorrhagic stroke, embolism systemic, deep vein thrombosis, pulmonary embolism, stable angina, unstable angina, myocardial infarction with/without ST segment elevation; and bleeding events (Yes/No, number and date): intracranial, digestive, genitourinary, gingival, nasal, pulmonary, articular-muscular, conjunctival.	x	x (NYHA classification, Charlson Index)
CHA2DS2-VASc (total score)		x
HAS-BLED (total score)		x
Clinical Frailty Scale		x
Previous vitamin K antagonist (VKA) treatment (yes/no), type (acenocoumarol or warfarin), start date and treatment duration		
Other concomitant treatments (Total number of current concomitant drugs; Type (Yes/No, number): ARB or ACE inhibitor, Beta-blocker, Calcium channel blockers, Diuretics, Amiodarone, Statin, Proton pump inhibitor, H2-receptor antagonist, Digoxin, NSAIDs, Dronedarone, Other antiarrhythmics, ketoconazole (systemic), cyclosporine, itraconazole	x	

Document: H:\HOR-Europe\2019\2512352 - Study on anticoagulation management - BI\Proyecto\Estadística\SAP\S AP_REBELD_version1.0_08072020.docx

Author: [REDACTED] Version Number: Version 1.0
Version Date: [08072020]

Template No.: RWI_TP_BIOS0013 Revision 1

Reference: RWI_WI_BIOS0015

Effective Date: 15Jun2018

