14.3.1 Patient's characteristics

Patient's characteristics at the time of the study visit will be summarized descriptively by current NOAC type. Patients will be also stratified by duration since the first NOAC initiation until the study visit date (>4 months / ≤ 4 months). All covariates related to patient's characteristics (refer to Section 11 , Table 3.) will be analyzed descriptively by NOAC type and by the duration since the first NOAC initiation. Standardized differences between Pradaxa® and other NOACs will be estimated for these covariates. For this, a minimum of 50 patients is required for each group.

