**Table 13. History of thromboembolic events according to current NOAC type**

		Dabigatran	Rivaroxaban	Apixaban	Edoxaban	Total	Standardized differences (Pradaxa® vs others)
History of thromboembolic events	Valid N No Yes N missing						
Number of total thromboembolic events	Valid N Mean (SD) Median (Q1-Q3) Min-Max N missing						
TIA	Valid N No Yes N missing						
Number of TIA	Valid N Mean (SD) Median (Q1-Q3) Min-Max N missing						
Ischemic stroke	Valid N No Yes N missing						
Number of ischemic strokes	Valid N Mean (SD) Median (Q1-Q3) Min-Max N missing						
Hemorrhagic stroke	Valid N No Yes N missing						

Document: H:\HOR-Europe\2019\2512352 - Study on anticoagulation management - BI\Proyecto\Estadistica\SAP\S AP_REBELD_version1.0_08072020.docx

Author:

Version Number:

Version 1.0

Version Date:

[08072020]

Template No.: RWI_TP_BIOS0013 Revision 1

Reference: RWI_WI_BIOS0015

Effective Date: 15Jun2018

		Dabigatran	Rivaroxaban	Apixaban	Edoxaban	Total	Standardized differences (Pradaxa® vs others)
Number of hemorrhagic strokes	Valid N Mean (SD) Median (Q1-Q3) Min-Max N missing						
Embolism systemic	Valid N No Yes N missing						
Number of embolism systemic	Valid N Mean (SD) Median (Q1-Q3) Min-Max N missing						
Deep vein thrombosis	Valid N No Yes N missing						
Number of deep vein thrombosis	Valid N Mean (SD) Median (Q1-Q3) Min-Max N missing						
Pulmonary embolism	Valid N No Yes N missing						
Number of pulmonary embolisms	Valid N Mean (SD) Median (Q1-Q3) Min-Max N missing						
Stable angina	Valid N No Yes						

Document: H:\HOR-Europe\2019\2512352 - Study on anticoagulation management - BI\Proyecto\Estadistica\SAP\S AP_REBELD_version1.0_08072020.docx

Author: [REDACTED]

Version Number:

Version 1.0

Version Date:

[08072020]

Template No.: RWI_TP_BIOS0013 Revision 1

Reference: RWI_WI_BIOS0015

Effective Date: 15Jun2018

		Dabigatran	Rivaroxaban	Apixaban	Edoxaban	Total	Standardized differences (Pradaxa® vs others)
	N missing						
Number of stable anginas	Valid N Mean (SD) Median (Q1-Q3) Min-Max N missing						
Unstable angina	Valid N No Yes N missing						
Number of unstable anginas	Valid N Mean (SD) Median (Q1-Q3) Min-Max N missing						
Myocardial infarction with ST segment elevation	Valid N No Yes N missing						
Number of myocardial infarctions with ST segment elevation	Valid N Mean (SD) Median (Q1-Q3) Min-Max N missing						
Myocardial infarction without ST segment elevation	Valid N No Yes N missing						

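### The standardized differences meant to assess channeling use study-visit covariates and one pooled contrast, so they do not isolate selection at the time of prescribing

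*Protocol*

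**What the plan says.** Protocol 9.9 describes channeling as confounding that arises when "a drug is preferentially prescribed to patients with different baseline characteristics". The same section states that "The choice of NOAC was done before the study visit", and then that "Standardized differences will be applied when assessing channeling bias".

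The calculation is set out in Protocol 9.7.1 and repeated in full in SAP 14.3.1. Standardized differences between Pradaxa and other NOACs "will be estimated for these covariates. For this, a minimum of 50 patients is required for each group". The covariates are those of "Table 3 Patient characteristics at the time of the study visit" (Protocol 9.3.3) and its SAP counterpart in section 11. Laboratory values come "from last available blood sample analysis". The risk scores are assessed at the visit.

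The mock tables that carry the statistic are SAP Tables 7 to 16. They are grouped by current NOAC and have one column for Pradaxa against the others. One of them is "History of thromboembolic events according to current NOAC type" (Table 13). It and its bleeding counterpart, Table 14, show yes/no and number of events with no time window. The SAP does collect timing, since its Table 3 lists "bleeding events (Yes/No, number and date" and the same for thromboembolic events.

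**The concern.** Channeling concerns who was given which drug. To assess it, the covariates should describe the patient when the drug was chosen. Here they describe the patient at a visit at least 3 months after NOAC treatment began, with no upper limit on that interval. They are grouped by the drug taken now, which may follow a switch.

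Two misreadings could result. If one NOAC has been used for longer, its users have had more time to age and to have events. The standardized difference could then look like selection of sicker patients where there was none. In the other direction, the single pooled contrast can be near zero when dabigatran users differ from users of two other NOACs in opposite directions.

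This is the only tool the plan names for channeling. SAP 8.1 plans no statistical method for handling bias, so nothing else would correct either misreading.

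**Working it through.** The documents give no planning figure for these standardized differences and no threshold for a relevant one. They also give no event rates or durations by NOAC. The timing is therefore checked by reading, and the size by illustration.

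**Timing of the rows in SAP Tables 7 to 16**
- *Fixed:* sex and the date of NVAF diagnosis cannot change after the choice.
- *Moves with time on drug:* age at the visit, and years since NVAF diagnosis, which SAP 7.2.5 runs to the visit date.
- *Can change after the choice:* weight, laboratory values, comorbidities, concomitant drugs, CHA2DS2-VASc, HAS-BLED and the Charlson index. The scores contain age and event items, so a later event can enter more than one row.
- *Accumulates:* thromboembolic and bleeding history, because no window is set.

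**Drift after the choice (all inputs assumed)**

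Let both groups have the same proportion b with a bleeding history when the drug is chosen, so the true difference is 0. With event rate r per year and t years on drug, the proportion with a history at the visit is

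p = 1 − (1 − b)·exp(−r·t)

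and the standardized difference is

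d = (p1 − p2) / √[(p1(1 − p1) + p2(1 − p2)) / 2].

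With b = 0.05 and r = 0.04:

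| Years on drug | p1 | p2 | d | d for r = 0.02 to 0.06 |
|---|---|---|---|---|
| 3 vs 3 | 0.157 | 0.157 | 0.00 | 0.00 |
| 3 vs 2.5 | 0.157 | 0.140 | 0.05 | 0.03 to 0.06 |
| 4 vs 3 | 0.190 | 0.157 | 0.09 | 0.06 to 0.11 |
| 5 vs 2 | 0.222 | 0.123 | 0.27 | 0.17 to 0.34 |

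Unequal rates have the same effect. With b = 0.10 and 3 years in both groups, 2% versus 4% per year gives p = 0.152 versus 0.202 and d = −0.13. A comparison of 2% with 5% per year gives 0.152 versus 0.225 and d = −0.19.

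**Pooling (all inputs assumed)**

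Take a covariate present in 30% on dabigatran and in 20%, 40% and 30% on the other three NOACs. The pairwise values of d are +0.23, −0.21 and 0.00.
- *Equal group sizes:* the pooled prevalence is 30%, so d = 0.00.
- *Weights 25/50/25:* 0.25·20 + 0.50·40 + 0.25·30 = 32.5%, so d = −0.05.
- *Weights 50/25/25:* 0.50·20 + 0.25·40 + 0.25·30 = 27.5%, so d = +0.06.

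**The case against.** The strongest reply is that the link to channeling is one sentence in a limitations section. The first secondary objective is to describe patients at the visit by current NOAC, and visit-time covariates are right for that. The visible SAP estimates the differences without mentioning channeling, and no clinical outcome is compared between NOACs for channeling to bias. This stands as a limit on the consequences. It does not remove the mismatch, because 9.9 still gives the statistic a purpose it does not serve.

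Three stronger readings are tempting, and the documents do not support them.
- *The differences will be distorted.* Drift needs unequal time on drug or unequal event rates. The documents give neither, and the illustration starts at 0.00.
- *Pooling makes an imbalance disappear.* Tables 7 to 16 print each NOAC in its own column. Only the summary number can hide opposite imbalances, and only if they run in opposite directions.
- *Tables 13 and 14 attribute past events to the current NOAC.* They cross-tabulate history. SAP Tables 46 to 49 show the treatment received at the time of each event. An event on an earlier NOAC is also valid history before the current one.

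Frailty is a weak example. The SAP lists it among the covariates, but its mock table (Table 42) has no standardized-difference column.

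Some content at initiation exists. The protocol abstract foresees variables at first NOAC initiation where available, and SAP Table 43 gives primary or secondary prevention at that time. No visible standardized difference uses either. SAP sections 14.4 and 14.5 and Table 44 are not visible, so nothing is inferred from them.

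**Conclusion.** The concern holds in a limited form. As visibly planned, the standardized differences describe how patients on dabigatran and on all other NOACs together differ at the visit. They do not isolate differences at the time of prescribing, which is what Protocol 9.9 says they will assess.

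Under the assumed 5% prior history and 2 to 6 bleeds per 100 years, the spurious difference runs from 0.00 with equal durations to 0.34 at 5 versus 2 years. Pairwise differences of about 0.2 in opposite directions can pool to between −0.05 and +0.06. These figures show what is possible and do not predict this study's data. The simple model also ignores switching after an event and the exclusion of patients who stopped NOAC treatment.

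The primary outcome and the visit-time description are unaffected. The change is worth making because this is the plan's only named check for channeling and most of the data needed are already collected.

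**What to change.** 1. Keep SAP Tables 7 to 16 as description, and label their standardized differences as differences at the study visit.
2. For channeling, add standardized differences on variables fixed or dated before the start of the current NOAC: age at start, sex, prior VKA, prior NOAC, time from NVAF diagnosis to that start, and any thromboembolic or bleeding event dated before it. The current NOAC start date and the event dates are collected. SAP 7.2.8 already derives the time from diagnosis to first NOAC, so for patients who switched only the end date changes.
3. Show dabigatran against each other NOAC where both groups have at least 50 patients, alongside the pooled contrast.
4. State in 9.9 which variables the channeling assessment can and cannot cover.

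No new data collection is needed, but the costs are real. Laboratory values, weight, scores and frailty at start are largely unavailable, so channeling is judged on fewer variables. Event dates depend on the charts. Some will be missing, and SAP 8.4 sets missing days to mid-month, so events near the start may fall on the wrong side. Some pairs may not reach 50 patients. At 50 versus 50, the approximate 95% limits around a difference near zero are ±1.96·√(1/50 + 1/50) = ±0.39, so small pairwise values should be read with caution.
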